8.2. Background Characteristics

8.2.1. Participant Disposition

A clear accounting of the disposition of all participants who enter the study will be provided, from screening to study completion. This analysis will be based on All Enrolled Set.

The summaries of participant disposition on all participants will include:

- Number of participants screened (HD and HP)
- Number of participants screen-failed (HD and HP)
- Number of participants enrolled (HD and HP)
- Number of healthy participants (HP) enrolled
- Number of participants randomized (HD)
- Number of HD participants randomized but not treated
- Number and percentage of HD participants received at least one dose of IP

- Number and percentage of HD participants completed full treatment period of IP
- Number and percentage of HD participants discontinued from IP and primary reason for premature IP discontinuation
- Number and percentage of participants (HD and HP) completed the study (completed Day 42 visit)
- Number and percentage of participants (HD and HP) discontinued from the study and primary reason for premature study discontinuation

Percentages will be calculated based on the participants that were randomized and received IP for HD participants, and percentages will be calculated based on all eligible participants for HP, accordingly. Treatment arm assignment of HD participants will be according to the randomized treatment. If a participant is rescreened because the participant has been a screen failure the first time, the status of the participant will be determined from the second screening. In the count of screened participants, this participant will be counted only once.

By-participant listings of disposition details will also be provided.

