5.2. Sample Size and Power

The study is designed to detect a difference between participants with HD and HP on HD-CAB composite score as the primary endpoint. Using a two-sided alpha level of 0.05, a sample size of at least 80 participants (40 HP and 40 participants with HD) would provide at least 80% power to detect a baseline difference in HD-CAB composite score assuming Cohen's D effect size equal to 0.63, which is in the range of effect sizes reported in the literature (Stout et al., 2014).

Using a CI approach for sample size estimation, and assuming a common SD of 1.51 in HD-CAB, a sample size of 32 evaluable participants with HD (16 per treatment arm) will provide 80% confidence level for estimating the population mean with 0.50 precision or margin of error.

Assuming a 20% dropout rate in participants with HD, a sample size of approximately 40 participants with HD will be randomized in a 1:1 ratio to SAGE-718 and placebo to obtain 32 evaluable participants with HD. Additional participants may be randomized if the dropout rate is higher than 20%.

Evaluable participants with HD are defined as those randomized participants who receive IP and have a valid baseline and at least 1 postbaseline efficacy assessment.

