7.3. Other Analysis Sets

All Enrolled Set: All Enrolled Set will include all randomized HD participants and all HP who meet the eligibility criteria and will be used to describe participant disposition and protocol deviations.

[REDACTED]
[REDACTED]

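### HD disposition percentages are computed over dosed participants only, so the any-dose row is always 100% and study-level retention is not per randomised participant

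*SAP*

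**What the plan says.** On the analysis set for disposition, SAP 8.2.1 states: "This analysis will be based on All Enrolled Set". SAP 7.3 defines that set: "All Enrolled Set will include all randomized HD participants and all HP who meet the eligibility criteria". Dosing is not a condition of membership.

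On the denominator, the same section 8.2.1 states: "Percentages will be calculated based on the participants that were randomized and received IP for HD participants". For healthy participants (HP) it uses all who are eligible. No other HD denominator is given for any row.

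The rows covered by that sentence include:
- "Number and percentage of HD participants received at least one dose of IP"
- completion of the treatment period and discontinuation of IP (HD only)
- completion of the study, defined by the Day 42 visit (HD and HP)
- "Number and percentage of participants (HD and HP) discontinued from the study and primary reason for premature study discontinuation"

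One further row, "Number of HD participants randomized but not treated", is a count with no percentage. HD arms are shown by randomised treatment.

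Protocol 13.1 describes disposition on the All Randomized Set. SAP 6.1 declares the replacement of that set by the All Enrolled Set, but it does not declare a denominator limited to dosed participants.

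**The concern.** The section names one population and divides by another. Three things follow from the text.

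1. The any-dose row carries no information, although it is the row that should show what fraction of randomised participants started treatment.
2. HD study completion and discontinuation are not expressed per randomised participant, which is the usual reading of a disposition table and the one that the named set implies.
3. The numerator is unstated. An undosed participant who leaves may or may not be counted as a study discontinuation. Two programmers could produce different tables, and in one of them the numerator would not be a subset of the denominator.

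In addition, the HD and HP columns of the same study-level rows are on different bases. What is at stake is the accuracy of reported retention, overall and by arm.

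**Working it through.** **Inputs.** 40 HD participants randomised, 20 per arm (Protocol 7.2; SAP 5.2). 32 evaluable and 20% dropout (SAP 5.2). Denominator rule from SAP 8.2.1. The number never dosed, *u*, is not given in the documents. It is an assumption, varied from 0 to 4. The total of 8 non-completers is also an assumption, and all undosed participants are taken to be among the 8.

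**Step 1: the plan's own figure.** 32 / (1 − 0.20) = 40, which matches the stated 40 randomised for 32 evaluable. The planning rate is therefore a proportion of those randomised.

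**Step 2: any-dose row.** With D = 40 − *u* dosed, the SAP rule gives D / D = 100.0% for every *u*. On the randomised basis the row is D / 40, which is 100.0, 97.5, 95.0, 92.5 and 90.0% for *u* = 0 to 4.

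**Step 3: study-level rows.** Discontinuation under the SAP rule is (8 − *u*) / (40 − *u*) if the undosed are left out of the numerator, or 8 / (40 − *u*) if they are kept in. Completion is 32 / (40 − *u*). On the randomised basis these are 8 / 40 = 20.0% and 32 / 40 = 80.0% for every *u*.

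| Never dosed (*u*) | Discontinued, undosed left out | Discontinued, undosed kept in | Completed |
|---|---|---|---|
| 0 | 8/40 = 20.0% | 8/40 = 20.0% | 32/40 = 80.0% |
| 1 | 7/39 = 17.9% | 8/39 = 20.5% | 32/39 = 82.1% |
| 2 | 6/38 = 15.8% | 8/38 = 21.1% | 32/38 = 84.2% |
| 3 | 5/37 = 13.5% | 8/37 = 21.6% | 32/37 = 86.5% |
| 4 | 4/36 = 11.1% | 8/36 = 22.2% | 32/36 = 88.9% |

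With the undosed kept in, completion and discontinuation sum to more than 100%: for *u* = 2, (32 + 8) / 38 = 105.3%.

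**Step 4: one arm.** With 20 randomised, 4 non-completers and 2 of those never dosed, discontinuation reads 2/18 = 11.1% or 4/18 = 22.2%, against 4/20 = 20.0%.

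**The case against.** **Few or none may be undosed.** Randomisation follows the eligibility checks on Day 1, and the first dose is taken under supervision at that visit (Protocol Table 1 footnotes). With *u* = 0 both bases agree. This stands as a limit on size. But SAP 8.1 provides a study-day rule for untreated randomised HD participants, so the plan foresees the case.

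**The counts are reported anyway.** The numbers randomised, dosed and randomised but not treated are all listed, together with by-participant listings. A reader can rebuild the any-dose percentage. The study-level percentages can be rebuilt from the table only if it is clear whether the undosed are in the numerator, and at present it is not.

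**A dosed denominator is sometimes right.** This stands for IP completion and IP discontinuation, which are questions about people who started IP. The two rows are complementary, so they should share one denominator.

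**No inference depends on it.** This also stands. The primary comparison uses the Full Analysis Set, which does not require dosing, and the safety summaries of HD participants use those who were dosed.

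**A stronger reading.** SAP 5.2 says: "Additional participants may be randomized if the dropout rate is higher than 20" per cent. A reader might infer that the 8.2.1 denominator could hide a breach of that threshold. The documents do not support this, for two reasons. First, randomising more participants is an operational decision taken during enrolment (Protocol 7.2 and 8.4.4), whereas SAP 8.2.1 governs a final-analysis table and no interim analysis is planned. Nothing links the table to the decision. Second, the 40-to-32 planning concerns loss of evaluable participants: those who receive IP and have a valid baseline and at least one postbaseline efficacy assessment. Someone who leaves after the Day 14 assessment is a study discontinuation and can still be evaluable. Protocol 7.2 speaks more loosely of early discontinuation, but the arithmetic rests on the evaluable definition. Neither denominator in 8.2.1 yields that rate.

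**Conclusion.** The inconsistency is real and minor. Two consequences follow from the text without any assumption: the any-dose row is fixed at 100%, and HD study completion and discontinuation are not on the randomised basis. The size depends on how many randomised participants are never dosed, which the documents do not give. For 1 to 4 of 40, under the assumptions above, discontinuation differs from the randomised-basis figure by 2.1 to 8.9 percentage points downwards (20.0 − 17.9; 20.0 − 11.1) or 0.5 to 2.2 points upwards (20.5 − 20.0; 22.2 − 20.0). The direction turns on the unstated numerator. With none undosed there is no effect.

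No test or confidence interval changes. The 20.0% in the illustration sets a scale and is not a test against the planned dropout. The point carries no implication for the decision to randomise additional participants.

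**What to change.** Amend the denominator sentence in SAP 8.2.1 as follows:

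- Use all randomised HD participants, by randomised arm, as denominator for the any-dose, study-completion and study-discontinuation rows.
- Keep undosed participants in the numerators of the study-level rows wherever they meet the row's definition.
- Keep dosed participants as the denominator for both IP completion and IP discontinuation, and label those rows accordingly.

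The cost is one sentence and a few row labels. No new data are needed. If the database is already locked, SAP section 2 has such a change documented in the clinical study report.

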8.2.2. Protocol Deviations

This analysis will be based on the All Enrolled Set.

Protocol deviations will be classified as “major” or “minor” on an ongoing basis by the clinical study team and sponsor.

Major protocol deviations are defined as those deviations from the protocol likely to have an impact on the participant’s right, safety, well-being, and/or the validity of the data for analysis. Minor protocol deviations include all deviations from the protocol excluding the major protocol deviations.

The number and percentage of participants with a major protocol deviation will be summarized by cohort and randomized treatment group. A by-participant listing of all protocol deviations will also be provided.

8.2.3. Demographics and Baseline Characteristics

This analysis will be based on the Safety Set and FAS.

Demographic characteristics (age, race, sex, ethnicity, childbearing status, civil/marital status, years of education, highest level of education, current employment status, and total years of employment) and baseline characteristics, such as height (cm), weight (kg), body mass index (BMI) (kg/m^2), and HD-CAB composite score, [REDACTED]

[REDACTED] and HD-CAB Trail making test B will be summarized by treatment group, overall and HP.

Baseline subgroups will be summarized for the following categories:

- Age (≤ 50 , > 50)

- Race (Black or African American, White, Other)
- Sex (Male, Female, Unknown/Undifferentiated)
- BMI (≤ 18.4 , $18.5\text{-}24.9$, $25\text{-}29.9$, $\geq 30 \text{ kg/m}^2$)
- Country (US, Canada)

■ [REDACTED]

■ [REDACTED]

- CAG expansion (<40 , ≥ 40)

■ [REDACTED]

- Previous use of ASO drug (Yes / No)

■ [REDACTED]

■ [REDACTED]

- Baseline Trail Making Test B (<240 , $=240$)
- Use of Antidopaminergic Medications (ADM see Appendix F for details) (Yes / No)

BMI will be calculated as weight (kg)/height (m^2).

By-participant listing of demographic and other baseline characteristics will also be provided.

8.2.4. Medical History

This analysis will be based on the Safety Set 1 and Safety Set 2.

Medical history at screening will be coded using the Medical Dictionary for Regulatory Activities (MedDRA) Version 25.1 and summarized using system organ class and preferred term on Safety Set by actual treatment group.

By-participant listing of medical history will also be provided.

8.2.5. Prior and Concomitant Medications

This analysis will be based on the Safety Set 1 and Safety Set 2.

Medications will be recorded at each study visit during the study and will be coded using World Health Organization-Drug dictionary (WHODrug-Global-B3) September 2022 B3.

All medications taken within 60 days prior to informed consent through the duration of the study will be recorded. Those medications started and stopped prior to the initiation of the start of IP for HD and day 1 for HP will be denoted “Prior”. Those medications taken prior to the initiation of the IP and continuing beyond the initiation of the IP, or those medications started at the same time or after the initiation of the IP will be denoted “Concomitant” for HD.

Those medications taken prior to day 1 and continuing beyond day 1, or those medications started at the same time or after day 1 will be denoted “Concomitant” for HP.

Medications will be presented according to whether they are “Prior” or “Concomitant” as defined above. If medication dates are incomplete and it is not clear whether the medication are concomitant, it will be assumed to be concomitant.

Missing or partial dates will be imputed for medication. Algorithm for missing or partial start /end date is documented in [Appendix D](#).

Concomitant medications are further categorized as on-treatment and post-treatment as follows:

On-treatment concomitant medications are those that have been used between first and last dose of IP (both inclusive) as well as medications started prior to first dose of IP and continue beyond the initiation of IP.

Post-treatment concomitant medications are those that have been started after the last dose of IP.

Concomitant medications will be summarized on Safety Set using Anatomical Therapeutic Chemical (ATC) level 1 and preferred term by actual treatment group.

By-participant listings of prior and concomitant medications, and concomitant procedures will also be provided.

8.2.6. Physical Examination

This analysis will be based on the Safety Set 1 and Safety Set 2.

Full physical examinations will be performed at Screening and Day 42 (± 2 days)/ET, and include assessment of body system (eg, head, eye, ear, nose, and throat [HEENT], heart, lungs, abdomen, and extremities) [REDACTED]

[REDACTED] At other visits (eg, Day 28 for participants with HD), brief physical examination will be performed including general appearance, cardiovascular, respiratory, gastrointestinal, and neurological systems.

Any abnormality in physical examinations will be interpreted by an Investigator as abnormal, not clinically significant (NCS); or abnormal and clinically significant (CS) which will be reported as an AE.

By-participant listing of physical examination will be provided.

8.2.7. Investigational Product Exposure

This analysis will be based on the Safety Set 1.

Total drug exposure (in mg), total exposure duration to IP (in days), and percent of planned exposure received (in %) will be summarized for the Safety Set by actual treatment group.

Total drug exposure (in mg) is defined as the total IP in mg for SAGE-718 that was taken during the study. Total drug exposure for participants randomized to placebo is zero unless the participant has taken SAGE-718 by mistake, in which case the total exposure comes from SAGE-718 exposure. If a participant skips a dose on any of the days, the dose taken is 0 mg.

Total exposure duration to IP (in days) is defined as the date of the last dose minus the date of first dose plus 1. Note that this does not exclude days when the dose has been missed.

Planned drug exposure (in mg) for completers is defined as

- a) $1.2 \cdot (\text{Study Day of Day 28 visit} - \text{Day of the first dose} + 1)$ mg, if Study Day of Day 28 visit is in 28 ± 2 window;
- b) 1.2·26 mg, if Study Day of Day 28 visit < 26 ;
- c) 1.2·30 mg, if Study Day of Day 28 visit > 30 .

Planned drug exposure (in mg) for non-completers is 1.2 mg times date of the last dose minus the date of first dose plus 1.

Percent of the planned exposure received is defined as the total drug exposure, divided by planned exposure, times 100.

By-participant listing of the extent of exposure will also be provided.

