P-values greater than or equal to 0.0001, in general, will be presented to four decimal places. P-values less than 0.0001 will be presented as “<0.0001”. P values greater than 0.9999 will be presented as “>0.9999”.

Confidence intervals will be presented to one more decimal place than the raw data.

All summaries and figures will be provided by treatment group – either by randomized treatment or actual treatment received depending on the analysis set being used. Actual treatment is defined as: SAGE-718 or Placebo.

Participants who are randomized to 1.2 mg treatment will be summarized under SAGE-718 group. For efficacy data analysis, participants’ data are analyzed by randomization assignment. For safety data analysis, participants’ data are analyzed per the actual treatment

received, and this is determined as follows: if a participant received any dose of SAGE-718 at any point of time, the participant is assigned to actual treatment of SAGE-718.

All participant data, including those derived, to support tables and figures will be presented in the participant data listings. In general, the participant data listings will be sorted by participant number and assessment visit and date (and time, if applicable). The treatment will be identified for each participant.

General definitions are defined as below:

- Baseline for participants with HD is defined as the last non-missing measurement prior to the first dose of IP, unless stated otherwise. If the time of an assessment is collected, baseline will be the latest assessment prior to first dose of IP administration time; if the time of an assessment is not collected, the assessment on Day 1 is assumed to be prior to dosing if the protocol mentions that this assessment needs to be before dosing, or it is collected as “pre-dose”.
- Baseline for HP is defined as the last non-missing measurement on or prior to Day 1.
- Study day 1 is defined as the date of randomization for untreated randomized HD participants or the date of first dose for treated HD participants.
- Study day 1 is defined as the date of completion of the baseline assessments for HP.
- Study day will be calculated relative to Study day 1.

If event is prior to Study day 1, then study day is calculated as:

$$\text{Date of Event} - \text{Date of Study day 1}$$

If event is after Study day 1, then study day is calculated as:

$$\text{Date of Event} - \text{Date of Study day 1} + 1$$

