8.2.8. Investigational Product Adherence

This analysis will be based on the FAS1.

IP adherence (%) is monitored using the medication adherence monitoring platform for all participants in the study. The IP adherence is defined as the number of capsules taken, divided by the number of capsules planned to be taken, times 100. For participants that complete the treatment period the planned number of capsules taken is

- a) $(\text{Study Day of Day 28 visit} - \text{Day of the first dose} + 1)$, if Study Day of Day 28 visit is in 28 ± 2 window;
- b) 26, if Study Day of Day 28 visit < 26 ;
- c) 30, if Study Day of Day 28 visit > 30 .

For participants that discontinue the treatment early, the planned number of capsules is (Last Dose Date – First Dose Date + 1).

IP adherence will be summarized on Safety Set by treatment group. Number and percentage of participants with IP adherence in categories (<80%, 80-100%, >100%) will be provided. IP adherence will be listed.

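### Minor: the percent of planned exposure in SAP 8.2.7 does not measure the share of the planned course in either arm: placebo is 0% by construction, and a SAGE-718 early stopper can score 100%

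*SAP*

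**What the plan says.** SAP 8.2.7 (Investigational Product Exposure) summarises three quantities by actual treatment group: total mg, days of exposure, and percent of planned exposure.

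- **Ratio:** "Percent of the planned exposure received is defined as the total drug exposure, divided by planned exposure, times 100".
- **Numerator:** mg of SAGE-718 taken, with a skipped day counted as 0 mg. "Total drug exposure for participants randomized to placebo is zero unless the participant has taken SAGE-718 by mistake".
- **Denominator, completers:** 1.2 mg times the days from first dose to the Day 28 visit, held between 26 and 30 days. There is no separate rule for placebo.
- **Denominator, others:** "Planned drug exposure (in mg) for non-completers is 1.2 mg times date of the last dose minus the date of first dose plus 1".

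SAP 8.1 sets the grouping: "if a participant received any dose of SAGE-718 at any point of time, the participant is assigned to actual treatment of SAGE-718".

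SAP 8.2.8 (Investigational Product Adherence) uses the same day spans but counts capsules: "The IP adherence is defined as the number of capsules taken, divided by the number of capsules planned to be taken, times 100". Its two branches begin "For participants that complete the treatment period the planned number of capsules taken is" (the same 26 to 30 rule) and "For participants that discontinue the treatment early, the planned number of capsules is" (first to last dose date, inclusive).

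The protocol Synopsis gives a 28-day treatment duration, and Protocol 9.4 has IP taken once daily from Day 1 through Day 28.

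**The concern.** A reader of an exposure table takes this percentage to mean how much of the intended course each group received. As defined, it does not answer that question in either arm.

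In the SAGE-718 group, the plan for a non-completer shrinks to the period actually treated. Stopping early then cannot lower the figure; only doses missed before stopping can. Completers are measured to the Day 28 visit, so one column mixes two quantities.

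In the placebo group, the numerator is a drug that its members by definition never took, so the column says nothing about placebo intake.

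Section 8.2.7 also leaves 'completers' undefined. Participants who stop IP are asked to stay for the remaining visits (Protocol 7.1.3), so someone can stop treatment and still complete the study. Two programmers could put that person in different branches.

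At stake is the reading of one descriptive column that supports the secondary objective of safety and tolerability. No endpoint uses it, and SAP 8.4 specifies no hypothesis tests on safety data.

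**Working it through.** The SAP states no numerical result for this measure, so there is no figure to reproduce. The check applies its definitions directly.

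**Inputs.** Dose 1.2 mg once daily and the planned-exposure rules (SAP 8.2.7); 28 planned daily doses (Protocol Synopsis and 9.4); actual-treatment rule (SAP 8.1).

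**Formula.** Percent = 100 × (1.2 × SAGE-718 doses taken) / planned mg. For a completer seen on Study Day 28, planned mg = 1.2 × (28 − 1 + 1) = 33.6.

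**1. Placebo group.** SAP 8.1 moves anyone with a SAGE-718 dose out of this group, so every numerator is 0.

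- Completer seen on Study Day 26, 28 or 30: 0/31.2, 0/33.6 or 0/36.0 = 0%.
- Stopper with last dose on Day 14: 0/16.8 = 0%.
- If planned placebo mg is instead read as zero, the ratio is 0/0. The SAP does not say this, and it would be equally uninformative.

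**2. SAGE-718 early stopper, no missed dose, classed as a non-completer.**

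| Doses taken | SAP 8.2.7 | Share of 28 planned doses |
|---|---|---|
| 7 | 8.4/8.4 = 100% | 7/28 = 25% |
| 14 | 16.8/16.8 = 100% | 14/28 = 50% |
| 21 | 25.2/25.2 = 100% | 21/28 = 75% |

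Missed doses do register: last dose on Day 14 with two missed gives 14.4/16.8 = 85.7%, against 12/28 = 42.9% of the course.

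**3. The other reading of 'completers'.** Take the 14-dose stopper who stays in the study and attends on Study Day 28. As a study completer, the denominator is 33.6 mg and the result is 16.8/33.6 = 50%. The same person scores 100% or 50% depending on the reading.

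**4. Relation to 8.2.8.** With n doses taken and p planned, 1.2n/1.2p = n/p, which is the adherence percentage. A treatment completer missing 3 of 28 doses scores 30.0/33.6 = 25/28 = 89.3% in both sections. This identity needs the treatment-completer reading, the same data source and the same analysis set, and it excludes anyone given the wrong product.

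**The case against.** The strongest reply is that the 100% figure rests on an interpretation. Study completion is the status the documents define most plainly (Protocol 7.6; the Day 42 visit in SAP 8.2.1), and SAP 8.2.1 counts completion of the IP treatment period separately. On a study-completer reading, early stoppers who stay in the study are measured to the Day 28 visit and the percentage does fall. This stands: the parallel wording in 8.2.8 favours the treatment-completer reading but does not settle it. It does not rescue the column, because the study-completer reading still leaves early withdrawals at 100% if they missed no doses, and placebo at 0%.

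A second reply is that the formula is written out, so a ratio over time on treatment is a disclosed choice. That would be fair if the label said so, but the label refers to the planned exposure.

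Three stronger readings are tempting, and the documents do not support them.

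- A reader might infer that early stopping disappears from the report. It does not. Total mg and exposure days are in the same section, IP discontinuations with reasons are in SAP 8.2.1, TEAEs leading to IP withdrawal are in 8.4.1, and capsule adherence in 8.2.8 covers placebo.
- A reader might apply the 20% dropout figure to estimate how far the group mean is inflated. In SAP 5.2 and Protocol 13.8 that figure takes 40 randomized to 32 evaluable, where evaluable means having received IP with a valid baseline and at least one postbaseline efficacy assessment. Someone who stops after 21 doses would ordinarily already have a Day 14 assessment and count as evaluable. No rate or timing of IP stopping is stated.
- A reader might conclude that the column adds nothing to 8.2.8. That holds only under the conditions in step 4 of the working. Section 8.2.8 cites an adherence monitoring platform and 8.2.7 names no source. Section 8.2.8 also opens with "This analysis will be based on the FAS1", a set requiring a postbaseline efficacy evaluation, whereas 8.2.7 uses Safety Set 1.

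**Conclusion.** The point holds and is minor. The percentage defined in SAP 8.2.7 does not describe the share of the planned course in either arm.

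- The placebo result (0%, or 0/0) follows from the stated numerator and the actual-treatment rule, whichever way completers are read.
- The 100% result for a SAGE-718 participant stopping after 7, 14 or 21 doses assumes that early stoppers are non-completers and that no dose was missed before stopping. The overstatement per participant is then 75, 50 or 25 percentage points against 28 doses.
- The undefined term is itself a defect, since it can move one participant between 100% and 50%.

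These are individual-level sizes; no group-level size can be drawn from the documents. The effect is confined to one column of a descriptive table.

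**What to change.** In SAP 8.2.7:

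1. Replace 'completers' with the term 8.2.8 uses, participants that complete the treatment period, and keep their 26 to 30 rule.
2. For treated participants who stop IP early, use the protocol's 28 once-daily doses as the planned denominator.
3. Compute the percentage from IP capsules taken, in both arms.
4. Keep total mg of SAGE-718 as a separate line, and flag and list anyone who took the wrong product. The flag matters because a placebo-randomized completer with one SAGE-718 capsule is counted under SAGE-718 and would show 28/28 = 100% by capsules, while the mg line shows 1.2 mg.

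In SAP 8.2.8, keep the ratio to own last dose and label it as adherence while on treatment. As a side note, 8.2.8 names both FAS1 and the Safety Set for one summary; the SAP should name one.

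**Cost.** SAP wording and one changed derivation. No new data are needed: Protocol 10.6 already records medication ID and capsules dispensed and returned. The percentage for early stoppers becomes less favourable. A small denominator difference remains: a completer seen on Day 26 with 26 doses scores 26/26 = 100%, while an early stopper with 26 doses scores 26/28 = 92.9%. For treatment completers without a dosing error, 8.2.7 will still equal 8.2.8 when both use the same data source and analysis set.
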